#### 11.1.2 Application to Independent Ethics Committee and/or Regulatory Authorities

It is the responsibility of the Principal Investigator (PI) to obtain approval of the CSP/CSP amendment(s) from the IEC. The study shall not begin until the required favorable opinion from the IEC has been obtained. The PI shall file all correspondence with the IEC in the Investigator file and copies of IEC approvals shall be forwarded to the Sponsor. Any additional requirements imposed by the IEC or RA shall be followed.

The collection, access to, processing, and transfer of protected health information or sensitive personal data shall be carried out in accordance with applicable rules and regulations.

### 11.2 Informed Consent Process

#### 11.2.1 Subject information and informed consent

The PI or his/her authorized designee must always use the IEC-approved subject information and Informed Consent Form and it must not be changed without prior discussion with the Sponsor and approval from the applicable IEC.

It is the responsibility of the PI or his/her authorized designee to give each subject prior to inclusion in the study, full and adequate verbal and written information regarding all aspects of the clinical study that are relevant to the subject's decision to participate throughout the study, e.g. explain the purpose and procedures of the study, the duration and number of expected participants, possible risks involved, and the opinion of the IEC. The subject shall be informed that the participation is confidential and voluntary and that the subject has the right to withdraw from the study at any time, without any effect on his/her future medical care, treatment or benefits to which the subject is otherwise entitled. The information shall be provided in a language clearly and fully understandable to the subject. The subject shall be given sufficient time to read and

 EST. 1981	Title 43CH2305 CSP Vital-Lido-Hand-2w	Doc id MA-57336
---	---	---------------------------

understand the Informed Consent Form and to consider participation in the study. Before any study-related activities are performed, the Informed Consent Form shall be personally signed and dated by the subject and the PI or his/her authorized designee responsible for conducting the informed consent process. The consent includes information that data will be collected, recorded, processed, and transferred to countries outside China. The data will not contain any information that can be used to identify any subject.

All signed Informed Consent Forms shall be filed in the Investigator file. The subject shall be provided with a copy of the signed and dated Informed Consent Form and any other written information.

The Investigator shall ensure that important new information is provided to new and existing subjects throughout the study.

## 12 Requirements on Adverse Events and Device Deficiency Reporting

### 12.1 Definition of Adverse Events and Reporting Requirements

#### 12.1.1 Definitions of Adverse Events (AEs)

An AE is any untoward medical occurrence, unintended disease or injury, or untoward clinical signs (including abnormal laboratory findings) in subjects, users or other persons\*, whether or not related to the study product.

This definition includes:

- Events related to the investigational product or the reference product
- Events related to the procedures involved

*\*For users or other persons, this definition is restricted to events related to the investigational product*

#### 12.1.2 Recording Instructions

AE will begin to be collected after ICF signed. Each subject will be questioned about AEs at each clinical visit following the screening visit. The question asked will be "Since your last clinical visit have you had any health problems?" Information on AEs can also be obtained from signs and symptoms detected during each examination or from a laboratory test, observations by the study personnel, subject diaries or spontaneous reports from the subjects.

When an AE is related to a device deficiency (refer to section 12.2), including technical device malfunction, the AE shall be recorded on the AE module in the eCRF and the technical complaint shall be reported separately on the clinical study complaint form.

Investigators, or other study personnel, will record all AEs in the eCRF, including:

- Event term (recorded in standard medical terminology and avoiding abbreviations),
- Description of event and affected area (if applicable),
- Start date (First day with symptoms)

 EST. 1981	Title 43CH2305 CSP Vital-Lido-Hand-2w	Doc id MA-57336
---	---	---------------------------

- Stop date (Last day with symptoms)
- Intensity (mild, moderate or severe according to definition in section 12.1.3)
- Seriousness (serious or not serious, according to definition in section 12.3)
- Causal relationship to study product and study product injection procedure (yes or no)
- Action taken (none, medication treatment, non-pharmacological treatment or other procedures/ tests, subject withdrawn)
- Outcome of the AE (ongoing, resolved, resolved with sequelae, death)

The AE module in the eCRF must be signed and dated by the Investigator.

#### 12.1.3 Intensity

For each reported AE, the intensity will be recorded. The following definitions of intensity are to be used:

**Mild:** A mild AE means awareness of symptoms or signs, but easily tolerated (acceptable).

**Moderate:** A moderate AE means enough discomfort to interfere with usual activity (disturbing).

**Severe:** A severe AE means incapacity to work or to do usual activity (unacceptable).

If the intensity changes over time the maximum intensity of the AE should be recorded.

#### 12.1.4 Causal Relationship and Seriousness

Each AE, serious as well as non-serious, will be assessed by the Investigator for causal relationship with the study product and its use (the injection procedure) and for seriousness (yes or no) of the event.

A two-point scale (Yes or No) will be used for causality assessments. The Investigators shall be asked to indicate a response to each of the following questions in the eCRF:

- “Do you consider that there is a reasonable possibility that the event may have been caused by the study product?” and
- “Do you consider that there is a reasonable possibility that the event may have been caused by the study *product injection procedure*?”

If any of these questions is answered Yes, the AE is considered related.

Each AE will also be assessed for causal relationship and seriousness by the Sponsor, in order to fulfil regulatory requirements.

#### 12.1.5 Reporting of Adverse Events

AE reporting on each subject will start after the ICF has been signed. The reporting will continue during each follow-up visit (including telephone contacts and extra visits between planned visits)

 EST. 1981	Title 43CH2305 CSP Vital-Lido-Hand-2w	Doc id MA-57336
---	---	---------------------------

until the last scheduled visit in the study.

**All AEs**, non-serious as well as serious, are to be reported as an AE in the eCRF.

#### 12.1.6 Follow-up of Unresolved Events after Study Termination and New Events after Study Termination

All serious as well as non-serious AEs with a causal relationship to the study product or treatment procedure with onset after subject participation in the study has ended shall be collected and reported to Sponsor on a paper AE form or in the post marketing AE form or SAE paper form if applicable. The events shall thereafter be followed up until resolved or considered chronic or stable, or for at least three months. Final outcome shall be reported on the AE follow up form.

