Study 05DF1206 is an open, non-comparative study on the efficacy and safety of treatment of acne scars with Restylane Vital Lidocaine. In this study, 12 subjects were enrolled for treatment of acne scars and surrounding skin with up to 4 mL of Restylane Vital Lidocaine in 3 treatment sessions spaced 4 weeks apart. The findings demonstrated improvements in the appearance of atrophic, depressed, facial acne scars and in the quality of the surrounding skin following three treatment sessions of Restylane Vital Lidocaine. For the investigator-reported GAIS, 92% of the subjects were assessed to be at least somewhat improved at week 4 and from week 8 to 28, 100% of the subjects were improved. At week 36, 75% of the subjects were satisfied with the structure of the skin compared to 8% at baseline before treatment. In all cases, the satisfaction was increased from week 12, when the treatment regimen was completed, until study end. In terms of safety, eight subjects reported at least one AE that was assessed by the investigator to be procedure-related, and the most common AEs were implant site nodule and implant site redness, each event reported by 5 subjects. All events resolved during the study. Subject diary data showed that the majority of subjects experienced injection-site reactions (such as bruising, redness, swelling, pain (including burn), tenderness, itching and bumps) after treatment. Frequency and severity of all symptoms decreased over time and the majority of the injection-site reactions were resolved within 14 days after each treatment session.

Study 05DF1211 is an evaluator-blinded, within-group, multi-center study of the effectiveness and safety of combined treatment with Azzalure, Restylane/Emervel fillers, and Restylane Skinboosters Vital Lidocaine compared with single treatment with either Azzalure alone (Group A) or Restylane/Emervel filler alone (Group B) in face. There were 61 subjects randomized (1:1) to either Group A or Group B. The study result revealed that the majority of subjects in the study population (83%) as well as in Group A (74%) and Group B (93%) separately, showed a superior

 EST. 1981	Title 43CH2305 CSP Vital-Lido-Hand-2w	Doc id MA-57336
---	---	---------------------------

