If an AE which, according to the Investigator's assessment, is related to the use of any of the study products and is still ongoing at the time of the withdrawal, such events shall be followed-up after the last study visit until resolved, assessed as chronic or stable, or for at least three months.

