10.1.2 Missing and Partial Dates Management

10.1.2.1 *Missing and Partial Dates of Adverse Events*

While every effort will be made to obtain complete information on every reported AE, imputation will be made for any respective missing AE data for the purpose of calculating onset time and duration. Dates will be presented as is in the listings.

The following date imputation rules will be used.

- Start Date
 - If start date is completely missing, it will be assumed that the AE started at the treatment date.
 - If the start date is missing the day, the treatment day will be used.
 - If the start date is missing the month, the treatment month will be used, provided it is on or after the subject's treatment date; otherwise, the subsequent month after the treatment date will be used (i.e., if treatment date is 15-DEC-2023, and AE start date is 01-UNK-2023 then start date becomes 01-JAN-2024).
 - If the start date is missing the year, the treatment year will be used provided it is on or after the subject's randomization date; otherwise, the subsequent year after randomization will be used.
- End Date
 - If end date is completely missing, it will be assumed that the AE is still ongoing and will not be imputed.
 - If the end date is missing the day, the last day of the month will be used (i.e., UNK-JAN-2024 becomes 31-JAN-2024)
 - If the end date is missing the month, the subsequent month after the start date will be used.
 - If the end date is missing the year, the year of treatment will be used (i.e., 01-JAN-UNK becomes 01-JAN-2024), provided it is after the start date; otherwise, the subsequent year after start date will be used.

10.1.2.2 *Missing and Partial Dates of Prior/Concomitant Therapies and Prior Aesthetic Procedures or Implants*

As no calculations on start and stop dates will be done, no imputation of missing or partially missing dates will be performed.

GALDERMA <small>EST. 1981</small>	Title 43CH2305 Statistical Analysis Plan	Doc id MA-59378
---	---	----------------------------------

Study Number 43CH2305
Statistical Analysis Plan

CONFIDENTIAL

Page 23 of 36
Final, 1.0, date 24APR2024

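### No stated follow-up rule covers a completer's related adverse event still ongoing at Day 15, although the heading of Protocol 12.1.6 announces one, and such events drop out of the SAP's duration summary

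*Protocol*

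**What the plan says.** Protocol 12.1.6 is headed "Follow-up of Unresolved Events after Study Termination and New Events after Study Termination", so it announces two groups of events. Its text deals with one: related events "with onset after subject participation in the study has ended". The next sentence, "The events shall thereafter be followed up until resolved or considered chronic or stable, or for at least three months", refers back to that group.

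Protocol 5.2.4 (Withdrawal of Subjects) holds the only other rule. A related event that "is still ongoing at the time of the withdrawal, such events shall be followed-up after the last study visit until resolved", or until one of the other end points listed there, is covered. The condition is withdrawal.

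Protocol 12.1.5 runs adverse event reporting "until the last scheduled visit in the study", which is Visit 4 at Day 15 (+3 days). Protocol 12.1.2 accepts ongoing as a recorded outcome.

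On the analysis side, SAP 10.1.2.1 states: "If end date is completely missing, it will be assumed that the AE is still ongoing and will not be imputed". SAP 10.6.1 summarises the duration of related events by SOC and PT with mean, SD, median and range. It names no method for ongoing events. Protocol 6.4.4 plans the same summary, split by treatment where applicable.

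**The concern.** Read literally, the rules leave one case out. A related event that starts after the study has a stated follow-up rule, and so does a related event ongoing when a subject withdraws. A related event that starts during the study and is unresolved at Visit 4 in a completer has none. The sample size section assumes 10% drop-out, so most subjects would be completers. The heading of 12.1.6 suggests that cover was intended.

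The gap carries into the analysis. An event with no end date has no duration. Longer events are more likely to be ongoing at the last visit, so the events that are left out are mostly long ones, and the reported durations tend to be too short. Follow-up lasts only two weeks, so this summary is one of the few places where a reader would look for persistence of local reactions.

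**Working it through.** **Step 1: coverage.** Setting the rules side by side:

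| Related event | Rule | Where |
|---|---|---|
| Starts after participation ends | Stated | Protocol 12.1.6 |
| Ongoing at withdrawal | Stated | Protocol 5.2.4 |
| Starts in study, ongoing at Visit 4, subject completes | None found | – |

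Two general duties remain. Protocol 7.7 makes monitors responsible for appropriate follow-up under NMPA requirements, without naming a duration, an end point or a population. Protocol 12.4 requires SAE reports to be completed, which does not reach non-serious events. Text is redacted near the adverse event and Visit 4 descriptions (Protocol 5.4 and 5.7.2.4) and cannot be checked. Section 12.1.6 itself shows no redaction.

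**Step 2: what the SAP does with such an event.** Duration needs a start date and an end date. A completely missing end date is not imputed, so there is no duration and the event cannot enter the mean, SD, median or range. The SAP does not say this outright; it follows from the two rules together.

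**Step 3: possible size.** The documents give no duration distribution for related events and no figure to reproduce, so this step is an illustration. The inputs are:

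- Median duration m of 2 to 4 days. This is the range that Protocol 9 reports for symptom duration in the earlier Chinese hand study.
- Lognormal shape with log-SD s of 0.8 to 1.2 (assumption).
- Onset delay exponential with mean 1 day (assumption).
- Cut-off 14 days after treatment, with events not ended by then excluded.

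The full-data mean is m × exp(s²/2). For m = 2, s = 0.8 this is 2 × exp(0.32) = 2.75 days. For m = 4, s = 1.2 it is 4 × exp(0.72) = 8.2 days. Simulation of one million events per row gives:

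| m | s | Ongoing | Mean, all | Mean, kept | Median, all | Median, kept | Mean of ongoing |
|---|---|---|---|---|---|---|---|
| 2 | 0.8 | 1.0% | 2.75 | 2.60 | 2.0 | 1.98 | 17.1 |
| 2 | 1.2 | 6.1% | 4.12 | 2.80 | 2.0 | 1.83 | 24.6 |
| 3 | 0.8 | 3.5% | 4.13 | 3.63 | 3.0 | 2.90 | 18.3 |
| 3 | 1.2 | 11.2% | 6.16 | 3.52 | 3.0 | 2.53 | 27.0 |
| 4 | 0.8 | 7.2% | 5.51 | 4.44 | 4.0 | 3.73 | 19.3 |
| 4 | 1.2 | 16.5% | 8.23 | 4.06 | 4.0 | 3.12 | 29.3 |

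The rows are internally consistent. In the last one, 0.8349 × 4.06 + 0.1651 × 29.3 = 3.39 + 4.84 = 8.23. The largest shift in the median is 4.0 − 3.12 = 0.88 days.

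**Step 4: what can be recovered.** In every row well under half of the events are ongoing and the full-data median lies far below 14 days, so a median that treats ongoing events as censored is estimable. The mean is not, unless end dates after Day 15 are obtained and used.

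**The case against.** The strongest reply is that this is a drafting mismatch with little consequence. Much of that reply stands.

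- A reader might infer that completers' events will be left unfollowed. The documents do not support that. A missing explicit rule is not a rule against follow-up, Protocol 7.7 sets a general duty, and the heading of 12.1.6 shows the intent.
- A reader might infer that no duration beyond about 15 to 18 days can ever be reported. That is wrong. Protocol 5.2.4 follows a withdrawn subject's events for longer. SAP 10.1.2.1 also imputes partial end dates: for a start on 2 May, an end date with only the day missing in May becomes 31 May, about 30 days.
- A reader might take the statement in Protocol 3.4 that "the majority of the injection-site reactions were resolved within 14 days after each treatment session" as evidence of many long events. It is diary data from a 12-subject facial acne-scar study. Protocol 5.4 lists diary events separately from adverse events, and the same account says that all the adverse events resolved during that study. Protocol 9.1.1 and 12.1.8 expect reactions to resolve within a few days.
- Exclusion of the longest events is a tendency only. A short event that starts on Day 14 is lost too.
- Ongoing events are not hidden. They stay in the subject and event counts, and their dates are listed.

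One part of the reply does not stand. It can be said that ongoing events are found by subtraction, because SAP 10.1.4 includes n in its default statistics. But SAP 10.6.1 gives its own list for duration, and that list omits n. Even with n shown, the mean and median would still rest on resolved events alone.

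**Conclusion.** The concern holds in a limited form. The heading and text of Protocol 12.1.6 do not match, and neither that text nor 5.2.4 covers a completer's related event ongoing at Visit 4. This rests on the readable text; a rule in redacted text cannot be ruled out. Under the SAP's date rules such events drop out of the duration summary, which then tends to be biased short.

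The size is unknown. Under the lognormal assumption with medians of 2 to 4 days it runs from negligible (1% ongoing, mean 2.75 to 2.60 days) to a halving of the mean (17% ongoing, 8.2 to 4.1 days), with the median moving by less than 1 day. The large effect needs the most skewed case. The medians describe symptoms in an earlier study, not related adverse events in this one. The summary is descriptive, and the primary endpoint, VAS at T0, is unaffected.

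**What to change.** **Protocol.** The sponsor must reconcile the heading and text of 12.1.6 with each other and with 5.2.4. Which follow-up rule applies is the sponsor's clinical decision.

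**SAP 10.6.1.** Make three additions:

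1. Beside each duration summary, report the number of related events ongoing at last contact.
2. Where event counts allow, estimate median duration with those events censored at last contact, for example by Kaplan–Meier. In sparse PT cells the count alone is enough.
3. State whether end dates obtained after Day 15 enter the locked database. Without this, a protocol correction alone would not repair the summary.

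The cost is a short protocol edit, one extra table column and a little analysis work. Any added site work depends on the rule the sponsor adopts.

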#### 12.1.7 Pregnancy

Pregnancy itself is not regarded as an AE.

If there is a pregnancy during the study period the subject must continue to be followed within the study and the outcome of pregnancy must be reported even if the expected date of delivery occurs after study completion.

A pregnancy confirmed during the study period must be reported by the Investigator on a pregnancy report form immediately upon acknowledgement be submitted to the Sponsor according to contact details specified in section 1.3. The report can be prospective or retrospective. Follow-up shall be conducted to obtain outcome information on all prospective reports.

Cases that led to fetal distress, fetal death or a congenital abnormality or birth defect are to be regarded as SAEs and shall be reported on the exposure *in utero* report form to the Sponsor immediately but no later than 24 hours after the Investigators awareness. These events shall be handled as SAEs during data processing. Other complications during the pregnancy that are related to the pregnant woman and fulfils any serious criteria, such as pre-eclampsia requiring hospitalization, shall be reported and handled as SAEs. Elective abortions without complications will not be reported as AEs.

#### 12.1.8 Anticipated Adverse Events

[figure not shown]
After the injection some common injection-related reactions might occur with both products. These reactions include bruising, redness, itching, swelling, pain (including burn) or tenderness at the implant site. Typically these reactions start on the day of treatment and resolve spontaneously within a few days after injection into the skin, as observed in the Chinese clinical study for Restylane Vital and in consistent with international results for the product.

### 12.2 Device Deficiency

#### 12.2.1 Definition of Device Deficiency

A device deficiency is defined as an inadequacy of a medical device with respect to its identity, quality, durability, reliability, safety\* or performance.

Note: Device deficiencies include malfunctions, use errors, and inadequate labelling.

 EST. 1981	Title 43CH2305 CSP Vital-Lido-Hand-2w	Doc id MA-57336
---	---	---------------------------

*\*Inadequacy of device safety refers to properties of the device which could have or have led to an AE.*

### 12.2.2 Recording Instructions

When a device deficiency is discovered the Clinical Study Complaint Form in the eCRF will be completed by the Investigator. The type of complaint shall be described and injury to the subject or user or unintended exposure to study product shall be reported as applicable. If an injury has occurred, an AE module or a SAE Form should be completed following instructions in section 12.4. If no SAE was experienced as a result of the device deficiency the Investigator shall assess whether or not the device deficiency could have led to an SAE if:

- Suitable action had not been taken,
- Intervention had not been made or,
- Circumstances had been less fortunate

The Sponsor will also make the same assessment in the Clinical Study Complaint Form.

### 12.2.3 Reporting Device Deficiency

The Investigator will complete the Clinical Study Complaint Form to the Sponsor using the contact details specified in section 1.3. A device deficiency that led to a SAE and any device deficiency that could have led to a SAE shall be reported within 24 hours after the Investigator's awareness in accordance to section 12.4.

In order to fulfil regulatory reporting requirements, all deficiencies with the study product must be assessed by both the Investigator and the Sponsor to determine if it could have led to a SAE.

If an SAE has resulted from a device deficiency or if either the Investigator or the Sponsor assesses that the device deficiency could have led to an SAE the event will be reported in accordance with Regulatory requirements, as applicable.

The deficient study product shall be kept, if applicable, by the study site until the QA complaints group has confirmed whether the product shall be returned to Sponsor for further study or if it can be destroyed at the study site.

